10. COMPENSATION

For each study visit, the study will cover the costs of economy class plane tickets for the primary research subject and for one parent. If the family prefers to drive to CCHMC, the study will reimburse the family at the standard CCHMC mileage reimbursement rate

for the distance from their home address to CCHMC as determined by Google Maps. Additionally, for the initial 12-month trial period the study will cover costs of the hotel rooms for up to 2 nights per study visit as well as the cost of transportation from and to the Cincinnati airport. A meal allowance of \$35 per individual per day will be covered. In the extension trial period, the study will cover cost of a hotel room for one night per study visit as well as a meal allowance of \$40 per individual per day. There will be no additional compensation for participation the study. The study will cover the costs of all medical evaluations detailed as part of this protocol that occur at CCHMC. GH and supplies will be provided to the subjects for free.

11. STATISTICAL CONSIDERATIONS

This is a pilot single arm study and thus no formal statistical comparison is planned. The outcome measures will all be descriptive. Therefore, we based our power calculations on our ability to confidently detect a positive effect on height SDS. We based the power calculation on our retrospective data. This sample size calculation is based on the following key assumptions: the mean first year response to GH of the 13 previously treated patients in our retrospective data was 0.407 SDS with a standard deviation of 0.343 SDS. We estimated that a sample size of 10 subjects will give us 90% power to demonstrate a change in SDS greater than zero at one-year post treatment initiation. Based on the retrospective data, we are 95% confident that the true mean response falls within the confidence interval of 0.19 to 0.62 SD. This sample size is feasible given the available patient population and estimated budget.

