Aggrecan, the protein encoded by the *ACAN* gene, is a critical proteoglycan component of the cartilage matrix, both in articular and growth plate cartilage, thus accounting for the dual phenotypic effects on both these types of cartilage. Consistent with this, homozygous mutations in *ACAN* in both mice and chicks severely disrupt growth plate function and impair bone elongation ^{2,3}. In both species, chondrocytes are tightly packed, with little intervening matrix. In chicks, there is evidence for abnormal Indian hedgehog, fibroblast growth factor, and bone morphogenetic protein signaling, leading to premature hypertrophic chondrocyte maturation². Because hypertrophic differentiation induces vascular invasion and ossification of growth cartilage⁴, these findings provide a likely explanation for the advanced bone age, premature growth cessation, and early epiphyseal fusion observed in individuals with *ACAN* mutations.

We published a follow up report describing 103 individuals from 20 families with confirmed mutations in *ACAN*⁵. This report describes more detailed clinical characterization of these patients. It notes some important features including a degree of subtle skeletal disproportion in many of the patients, as well as the presence of joint disease in 12 of the 20 families. We also described the growth pattern of patients with *ACAN* deficiency and note that there is progressive deterioration in the height standard

deviation score (SDS) because of the bone age advancement and premature epiphyseal fusion. Most relevant to the current ongoing trial, we described the response to GH treatment in 14 children treated with GH for at least 12 months. The average gain in height SDS was +0.4 after one year of treatment.

While this recent report is quite helpful to the practicing clinician, there are several key limitations. First, the patients were all assessed by different physicians at different centers. Second, the patients were treated with different GH regimens and six subjects were treated with either a gonadotropin releasing hormone (GnRH) analog or aromatase inhibitor (AI) in addition to GH. Third, all the data was collected via a retrospective chart review and thus is less reliable than prospectively collected research grade data. Finally, there was no standardized formal assessment of joint disease or the effects of GH on musculoskeletal complaints.

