4. SPECIFIC OBJECTIVES

Primary Objective:

- Describe the effects of one year of GH therapy on growth parameters in pre-pubertal children with ACAN deficiency, followed by describing the effects of continued treatment for another two years provided the objectives for the first year of GH therapy have been reached.

Secondary Objective:

- Describe additional clinical features of ACAN deficiency, in particular the degree of joint involvement, in the affected children and their affected first-degree relatives.

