 - G. Note – ADHD treated with a stimulant and treated hypothyroidism with a normal TSH will NOT exclude the subject from participating in the trial.
5. Malnutrition – Defined as a BMI <5th percentile (CDC growth charts)
6. Any clinically significant abnormality on screening laboratory tests as determined by the principal investigator.
7. Known or suspected allergy to trial medication, excipients, or related products.
8. Contraindications to study medications, worded specifically as stated in the product's prescribing information.
9. The receipt of any investigational drug within 90 days prior to this trial.

Withdrawal Criteria

The subject may withdraw at will at any time. The subject will be withdrawn if she becomes pregnant or intends to become pregnant. This should not be an issue as all subjects are pre-pubertal at onset of the trial.

Subject Replacement

If a subject is withdrawn from the study at any point, an additional subject will be recruited to meet our goal of 10 subjects completing 1 year of the study.

Rationale for Study Population

If a subject is withdrawn from the study at any point, an additional subject will be recruited to meet our goal of 10 subjects completing one year of the study. This has been reached. Any future drop out from the study will not be replaced by new recruitment as all 10 subjects are past the one-year treatment mark.

Subject Recruitment/Consent

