6. EXTENSION TRIAL

Background and Preliminary Results

As stated in our initial study protocol, patients demonstrating a year-1 increase in height SDS $> + 0.3$ will qualify to enroll in the extension trial, which will allow continuation of GH therapy for another two years, while using the same GH dosing protocol as for year 1. Of the five patients receiving GH therapy for at least six months, results from their 6-month study visits yield a favorable growth response. The annualized mean height velocity for this group is 9.4 cm/yr (range, 7.4 to 11.2 cm/yr). The annualized mean increase in height SDS is $+ 0.8$ (range, $+ 0.5$ to $+ 1.4$). Even the lowest responder achieved a gain in height SDS of $> +0.3$ (namely, $+ 0.5$ SDS), and thus qualifying for further treatment with GH as part of the study's extension trial requirements. All families have shown good practice adherence with both the GH injections, and the follow-up study visits so far. At this point, GH therapy is not FDA-approved for ACAN deficiency associated growth failure. There are, to our knowledge, no other trials for this disorder available to the patients with ACAN deficiency.

Specific Objective for the extension trial

Primary objective:

- Describe the continued effects (beyond year 1) of GH therapy on growth parameters in pre-pubertal children with ACAN deficiency.

Secondary objective:

- Continue to describe features of joint involvement, as noted on physical exam or history, in patients with ACAN deficiency receiving continued GH treatment - to provide additional insights into the underlying joint pathophysiology present in ACAN deficiency.

Study Design and Methods

Study Hypotheses:

1. Continued treatment with GH in children with ACAN deficiency will result in ongoing catch-up growth due to increased growth velocity.
2. Early joint pathology demonstrated on prior MRI will be evident on clinical examination of affected subjects.

Endpoints:

- A. Primary Outcome – Change in height SDS from 12 to 36 months, and overall delta height SDS from start of therapy to 36 months.
- B. Secondary Outcomes
 - a. Height velocity in cm/year calculated for each year of the trial.
 - b. Change in height velocity during years 2 and 3 of GH therapy.
 - c. Change in bone age divided by change in chronological age for each year of continued therapy.
 - d. Change in whole body bone mineral density adjusted for height at 24 and 36 months.
 - e. Frequency of adverse events as defined below.

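### Does the retrospective 95% interval of 0.19 to 0.62, printed beside a power claim with no stated test, need correcting?

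*Combined protocol and SAP*

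**What the plan says.** Section 11 opens with "This is a pilot single arm study and thus no formal statistical comparison is planned" and makes all outcome measures descriptive. It then sizes the study from retrospective data: the mean first-year response of the "13 previously treated patients in our retrospective data was 0.407 SDS with a standard deviation of 0.343 SDS". From this it concludes that ten subjects give "90% power to demonstrate a change in SDS greater than zero at one-year post treatment initiation". It also states, as a result drawn from the retrospective data, that "we are 95% confident that the true mean response falls within the confidence interval of 0.19 to 0.62 SD".

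No test, significance level or sidedness is attached to the power figure. No confidence interval is specified for the trial's own mean change.

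Three other places bear on the point:

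- Section 3 describes "the response to GH treatment in 14 children treated with GH for at least 12 months", with an average gain of +0.4 height SDS after one year.
- Section 4 frames the primary objective descriptively: "Describe the effects of one year of GH therapy on growth parameters in pre-pubertal children with ACAN deficiency". Section 5 fixes the primary outcome as the change in height SDS from baseline to 12 months.
- Section 5 reports that "all 10 subjects are past the one-year treatment mark", and Section 6 says of the first five patients that "results from their 6-month study visits yield a favorable growth response".

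**The concern.** Three things in one short paragraph invite doubt.

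First, a reader who computes the interval from the mean, SD and number printed beside it gets 0.20 to 0.61 and not 0.19 to 0.62. A planning figure that cannot be reproduced raises the question of whether the mean, the SD or the number of patients is right, and the first two drive the power calculation.

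Second, power has no meaning without a decision rule, and the section gives none while saying that no comparison is planned. Results were already accumulating when this version was written, so an open criterion for a change above zero could in principle be settled after the data were seen.

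Third, 13 patients in one section and 14 in another suggests that the planning data and the published data may not be the same set.

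**Working it through.** **Inputs (Section 11).** Mean m = 0.407, SD s = 0.343, retrospective n = 13, planned n = 10, printed interval 0.19 to 0.62, printed power 90%. The test is not stated. I assume a one-sample t-test of the mean change against zero and show how the answer varies.

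**1. The interval from the printed inputs.** Formula: m ± t(0.975, n−1) × s/√n.

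- Standard error: 0.343/√13 = 0.0951.
- Half-width: 2.179 × 0.0951 = 0.2073.
- Interval: 0.1997 to 0.6143. To the nearest hundredth this is 0.20 to 0.61. Rounded outward (lower limit down, upper limit up) it is 0.19 to 0.62, the printed pair.
- With the normal quantile the interval is 0.2205 to 0.5935, which does not match.

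**2. Rounding of the inputs.** Letting the mean run over 0.4065 to 0.4075 and the SD over 0.3425 to 0.3435 moves the lower t limit only between 0.1989 and 0.2005. Rounding of the inputs alone therefore does not produce 0.19.

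**3. Other routes to the printed pair under ordinary rounding.**

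| Basis | Interval |
|---|---|
| n = 10, normal quantile | 0.1944 to 0.6196 |
| n = 12, t | 0.1891 to 0.6249 |
| n = 13, t, if 0.343 was computed with divisor n, so the sample SD is 0.343 × √(13/12) = 0.357 | 0.1913 to 0.6227 |
| n = 14 (the Section 3 count), t | 0.2090 to 0.6050, no match |

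Outward rounding is the only candidate found that uses nothing beyond the printed n, mean and SD. The document does not say which route was taken.

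**4. The power claim.** Standardised effect: 0.407/0.343 = 1.187. Noncentrality at n = 10: 1.187 × √10 = 3.75. Power from the noncentral t distribution:

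| Rule | n = 8 | n = 9 | n = 10 |
|---|---|---|---|
| Two-sided 5% | 82.0% | 87.5% | 91.5% |
| One-sided 5% | 91.4% | 94.4% | 96.5% |
| Two-sided 1% | 50.0% | 59.8% | 68.4% |

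Ten is the smallest number that reaches 90% under a two-sided 5% test, which is the same as a two-sided 95% t interval excluding zero. A one-sided 5% test would have needed only eight, and a two-sided 1% test does not reach 90% at ten. The printed combination of 90% and ten therefore fits the conventional rule. If the SD is really 0.357, power at ten is 89.3%.

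**5. What depends on the interval.** The power calculation uses the mean, the SD and the planned number, and the interval does not enter it. The response rule for the extension in Section 6 applies a threshold of +0.3 SDS to each subject and uses neither the interval nor the group mean.

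**6. 13 against 14.** Section 3 gives an average gain of +0.4 in 14 children and Section 11 gives 0.407 in 13 patients. To the precision printed, the means agree.

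**The case for a change.** The best argument for a change is that the power statement is the plan's one inferential claim and its criterion is open. The choice is not neutral: at ten subjects, power runs from 68.4% to 96.5% across the rules shown above. With every subject past one year, the endpoint data may already exist. One sentence naming a two-sided 95% interval for the mean change would remove the doubt. A check of the source data would also settle whether 0.343 is a divisor-n SD, in which case power falls just under 90%.

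Part of this stands. The basis of the power figure is unstated, the route to the interval is undocumented, and 13 against 14 is unexplained. Outward rounding is itself only a possibility, and it sits a little oddly beside a mean and SD given to three decimals.

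It does not carry as far as a change. Only the conventional two-sided 5% rule makes ten the smallest number with 90% power, so the missing assumption can be recovered. The outcome and its time point are fixed, which leaves little analytic freedom, and a descriptive pilot can use power to choose its size without committing to a decision rule. A criterion added now would come after all ten subjects had passed the 12-month endpoint, so it could not restore prespecification. The divisor-n reading would move power from 91.5% to 89.3%, in a study whose ten subjects are already enrolled and past one year.

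**Conclusion.** No change to the plan follows. At worst the printed interval carries a clerical slip of about 0.01 SDS at each end, and it may only be outward rounding. Both versions exclude zero, and neither feeds the sample size or any conclusion. The 90% power is sound at 91.5%, assuming a two-sided 5% one-sample t-test with the printed mean and SD. It would be 89.3% if the SD was computed with divisor n, which the documents cannot settle. The unstated test and the 13 against 14 patients are gaps that an analyst fills sensibly: summarise the 12-month change in height SDS with its mean, SD and a 95% t interval. At the planning SD that interval would have a half-width of 2.262 × 0.343/√10 = 0.245 SDS. Followed as written, the plan still gives a sound descriptive result.

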12. DATA HANDLING AND RECORD KEEPING

All data will be collected in standardized case report forms. Forms will be kept in a locked cabinet in a secure location within the Endocrine department. Only the PI and study coordinator will have access to the forms. Review of all CRFs for completion will be done within 1 week after each study visit.

13. ETHICS

Written informed consent will be obtained from all subjects as well as written assent in subjects aged 11 years or older as detailed above. Consent processes will comply with all guidance and regulations of Cincinnati Children's Hospital Medical Center.

All subjects will be assigned a coded ID and all forms will only contain the coded ID. The code linking the ID with identifiable information will be kept on a password protected secure server as part of the Cincinnati Children's Hospital Medical Center research computing network. Only the PI and approved study personnel will be given access to this code.

The study will be conducted in accordance with the Declaration of Helsinki and will be conducted in accordance with the ICH GCP guidelines. [name], the sponsor-investigator, will comply with all applicable regulatory and legal requirements, ICH GCP

guidelines and the Declaration of Helsinki in obtaining and documenting the informed consent.

14. LIABILITY AND SUBJECT INSURANCE

As noted above, during and following a subject's participation in trial, [name] and Cincinnati Children's Hospital Medical Center will provide adequate medical care to the study subject for any study-related adverse events, including clinically significant laboratory values related to the study. This medical care for study subjects will be provided regardless of their insurance status.

[name] will be responsible for the conduct of the study and agrees to defend, indemnify, and hold harmless Novo Nordisk, any of its parent companies, affiliates, or subsidiaries, and their respective officers, directors, employees, agents, representatives, distributors, salespersons, customers, licensees, and end-users from and against any claim, suit, demand, loss, damage, expense or liability imposed by any third party arising from or related to: (a) any breach of [name] obligations or representations; or (b) [name] negligent or grossly negligent use or willful misuse of the study drug, the results, or services derived therefrom. This indemnification shall not apply in the event and to the extent that a court of competent jurisdiction or a duly appointed arbiter determines that such losses or liability arose as a result of Novo Nordisk's gross negligence, intentional misconduct, or material breach of its responsibilities.

15. PUBLICATION PLAN

[name] intends to publish the results of this trial within 12 months after completion in a peer-reviewed medical journal. He will also present the results of the trial at a national meeting such as the Endocrine Society or Pediatric Endocrine Society annual meetings. This trial is registered on clinicaltrials.gov.

[name] is currently a co-investigator. He was involved in the development of the initial study protocol, but not in the development of the extension studies. He does not have access to the raw study data. He will be involved in the development of abstracts/manuscripts that come out of the studies, and therefore will be exposed to deidentified growth and laboratory data from the studies. None of the study funds go towards [name] involvement in the study.

16. STUDY TIMELINE

IRB approval and an IND will be obtained prior to study initiation. We anticipate that it will take 6-18 months to recruit 10 eligible subjects. The study will then take an additional 36 months for the final patient to complete three years of treatment. Eligible subjects that are willing to enroll in the extension trial will come in for their final study visit in 2021 or 2022.

